#### Statistical Power

To conservatively calculate power for our main outcome (CVD risk score) we estimated 60 clinics with >35 high-CVD risk patients, randomized to two arms; then, using means and standard deviations for this measure from previous studies, we varied effect size associated with the group x time interaction and intraclass correlation. We examined a 1.5%, 2%, 3% greater absolute reduction in risk score over time in intervention vs. control CHCs. Aggressive management can reduce 10-year CVD risk by an absolute 4-5% in high-risk patients in a short time. We do not expect so large an effect and have power to detect smaller effects. **Supplement Addendum (Aim 2b).** This is a 2x2 repeated measures design with two groups of subjects measured at two time points. The primary goal is to compare change across time in group 1 (inperson index encounters) to change across time in group 2 (VC index encounters). A conservative estimate (based on preliminary results from the parent study) of 6000 patients in group 1 and 6000 in group 2 achieve 100% power to detect a difference in mean changes in CVD risk score of 5.0, with a standard deviation of 9.1 at the first time point, a standard deviation of 9.1 at the second time point, and a correlation between measurement pairs of 0.200. The significance level (alpha) is 0.050 using a two-sided, two-sample t-test.

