## Clinic Identification, Recruitment & Assignment

Clinics will be included in the recruitment pool for this study if they (1) provide primary care to adults with high CVD risk annually, and (2) have been using OCHIN's EHR for at least 18 months. Once all clinics have been recruited as outlined in Section 5.e., they will be assigned to either arm 1 or arm 2. Clinics were grouped based on the baseline number of encounters each service area had, percent of patients with hypertension, and percent of patients who use tobacco. Five randomly generated groupings were created and the grouping that created the most even distribution across both Arms was then selected to assign service areas and the clinics within each service area to an Arm.

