### **Intent to Treat Analysis**

Differences in change in outcomes will assessed using multi-level mixed models. Intra-class correlation coefficients will be obtained at the patient, clinic, and CHC organization levels for each outcome showed that much organization-level variance could be attributed to the clinic level. Thus, clustering was accounted for by random effects for clinic and patient, and a fixed effect for organization. Analyses will adjust for fixed effects: distribution of eligible patients by age, race / ethnicity, gender, rural / urban status, and federal poverty level (FPL) at index visit; number of ambulatory visits during the follow-up period; and time from index to last visit. These variables were selected *a priori* and will be confirmed by descriptive analyses, to determine whether there are significant differences between baseline intervention and control organization and patient characteristics. After checking distributions, negative binomial mixed-models or poisson mixed-model will be used for reversible risk analyses, and linear-mixed models for all other outcomes.

Patients diagnosed with diabetes during the follow-up period will be excluded from reversible risk analyses because diabetes might be diagnosed more often with CDSS use. Presence of diabetes raises reversible risk estimations even if CVD risk factor control was addressed; this exclusion will remove the possibility of confounding based on likelihood on new diabetes diagnosis.

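### The ITT model for change in reversible risk omits the patient's index risk as a covariate, giving up precision that data already in hand would recover

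*Combined protocol and SAP*

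**What the plan says.** **Analysis model.** The Intent to Treat Analysis section assesses differences in change with multilevel mixed models. Clinic and patient are random effects and organization is a fixed effect. The covariates, described as chosen a priori, are age, race/ethnicity, gender, rural/urban status and poverty level at the index visit, ending with "number of ambulatory visits during the follow-up period; and time from index to last visit". Index reversible risk is not listed. Reversible risk is to be modelled by a negative binomial or Poisson mixed model, and other outcomes by linear mixed models.

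**Index risk is available.** The Quantitative Data section has risk calculated at the index visit and at each follow-up encounter. The Effect of Treatment on the Treated section includes the baseline value of the outcome among its matching variables and stratifies the reversible-risk analysis by baseline risk.

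**Power.** For Aim 1 the size is given as follows: "we estimated 60 clinics with >35 high-CVD risk patients, randomized to two arms". The SDs are attributed to earlier work that is not shown. Of the remaining inputs the paragraph says only: "we varied effect size associated with the group x time interaction and intraclass correlation". The effects considered are 1.5, 2 and 3 points: "We examined a 1.5%, 2%, 3% greater absolute reduction in risk score over time in intervention vs. control CHCs". The comparison figure is "Aggressive management can reduce 10-year CVD risk by an absolute 4-5% in high-risk patients in a short time", and the paragraph concludes "We do not expect so large an effect and have power to detect smaller effects". No Aim 1 SD, correlation, ICC, alpha or resulting power is given. The only printed variance inputs (SD 9.1 at both times, correlation 0.200) belong to the Supplement's Aim 2b calculation.

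**Assignment.** The chosen grouping was "selected to assign service areas and the clinics within each service area to an Arm". The number of service areas is not stated.

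**The concern.** The primary question is a between-arm difference in change in risk. Three standard linear analyses answer it: compare change scores, compare follow-up values alone, or compare follow-up values adjusted for the index value. The third is never less precise than the other two in large samples. It also removes the effect of chance imbalance in index risk between arms.

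The section speaks of differences in change and the power paragraph frames the test as group by time, so the likeliest reading is a change-score contrast. If correlation over time is low, that contrast subtracts a noisy baseline in full and inflates the variance. The stake is precision: a wider interval for the primary effect than the collected data require, which matters most for the 1.5 and 2 point effects the plan examined.

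**Working it through.** **1. The one power figure the plan prints.** The Supplement has 6,000 per group, a difference in mean change of 5.0, SD 9.1 at both times, correlation 0.200 and two-sided alpha 0.05.
- SD of change = 9.1 × √(2 × (1 − 0.2)) = 9.1 × √1.6 = 11.51.
- SE = 11.51 × √(2/6000) = 0.210, and 5.0/0.210 = 23.8, so power is 100%. The stated figure reproduces. Aim 1 has no printed power to reproduce.

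**2. Why a repeated-outcome model does not recover the loss.** Take two time points, a patient random intercept and free terms for arm, time and arm × time. The interaction estimate is then the difference between arms in mean follow-up minus mean index value, with the index difference subtracted in full. I confirmed this on one simulated linear data set (400 per arm, SD 9.1, correlation 0.2, no clinic effect):

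| Analysis | Estimate | SE |
|---|---|---|
| Random-intercept model, arm × time | −2.94 | 0.809 |
| Simple change score | −2.94 | 0.809 |
| Adjusted for index value | −2.59 | 0.633 |
| Repeated measures, arms constrained equal at index | −2.59 | 0.634 |

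**3. Size of the gain.** With equal SD σ at both times and correlation ρ, the patient-level variances are:
- change score: 2(1 − ρ)σ²
- follow-up only: σ²
- adjusted for index: (1 − ρ²)σ²

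At ρ = 0.2 these are 1.60, 1.00 and 0.96 times σ². Adjusted against change score is 0.96/1.60 = 0.60, a 40% reduction. The SD falls from 11.51 to 9.1 × √0.96 = 8.92.

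The ratio of adjusted to change-score variance is (1 + ρ)/2. At ρ = 0.5 it is 0.75 (a 25% reduction), and at ρ = 0.8 it is 0.90 (10%).

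**4. Power.** Inputs:
- 60 clinics, from Statistical Power, split 30 per arm (assumption).
- 35 patients per clinic, the floor of the stated range, so 1,050 per arm.
- SD and correlation borrowed from the Supplement (assumption).
- Alpha 0.05 two-sided (stated for the Supplement only).
- ICC assumed over 0 to 0.10, and taken as equal for both analyses.

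SE = SD × √(2 × (1 + 34 × ICC)/1050), with power from the noncentral t on 58 df. At ICC 0.05 the design effect is 1 + 34 × 0.05 = 2.7. The SE is 0.825 for the change score and 0.639 adjusted.

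| ICC | Change score: 1.5 / 2 / 3 points | Adjusted: 1.5 / 2 / 3 points |
|---|---|---|
| 0 | 84 / 98 / 100% | 97 / 100 / 100% |
| 0.01 | 72 / 92 / 100% | 91 / 99 / 100% |
| 0.03 | 54 / 79 / 99% | 76 / 95 / 100% |
| 0.05 | 43 / 66 / 95% | 64 / 87 / 100% |
| 0.10 | 29 / 46 / 80% | 44 / 67 / 95% |

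At ICC 0.05 the difference detectable with 80% power falls from 2.35 to 1.82 points. Solving for the largest ICC that keeps 80% power (range: t to normal approximation):

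| Effect | Change score | Adjusted |
|---|---|---|
| 1.5 points | 0.003–0.004 | 0.024–0.026 |
| 2 points | about 0.03 | 0.066–0.070 |

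**The case against.** **A reader might infer that the power sentence is wrong, or that the trial is underpowered at 1.5 and 2 points. The documents do not support that.**
- Aim 1 used SDs from earlier studies that are not shown. The 9.1 and 0.200 are the Supplement's.
- With those values and no clustering, power at 1.5 points is about 84%. Any shortfall comes from ICCs the plan does not print.
- The sentence promises power only below 4–5 points. Three points satisfies it up to an ICC of about 0.10 with 60 clinics.
- Clinics and patients per clinic are minimums. At 200 patients per clinic (12,000 Supplement patients over 60 clinics, an assumption), change-score power at 1.5 points is about 98% at ICC 0.01 and 88% at 0.02.
- Assignment by service area may leave fewer independent units than 60, which would lower power, but without a count the effect cannot be sized.

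**On adjustment, the other side has four arguments.**
- *Index risk may enter as a repeated outcome.* True, but step 2 shows this returns the change-score contrast unless the arms are constrained equal at index. The section does not mention such a constraint.
- *The treatment-on-treated analysis handles baseline.* It does, but that is a separate, non-randomized comparison.
- *The gain depends on unprinted values.* This stands. It shrinks as correlation rises. If the model in fact used follow-up values alone, adjustment would save only 4% at correlation 0.2 (0.96 against 1.00), although 25% at 0.5.
- *Normal theory and a common ICC are approximations.* This also stands. Reversible risk is to be fitted with a count model. Stable clinic differences cancel in change scores, so the ICC of change may be below that of the level, which would narrow the power gain.

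**Conclusion.** The covariate omission holds. The ITT model leaves out index reversible risk while the plan computes it for every patient and matches on baseline outcome elsewhere. Under the change-score reading, adjustment cuts patient-level residual variance by 40% at correlation 0.2, and in the illustrated case raises power at 2 points from about 66% to 87%. Those sizes rest on the Supplement's SD and correlation, the planning floor of 60 × 35, an assumed ICC of 0.05 common to both analyses, and normal theory. The direction does not: in the large-sample linear setting the adjusted analysis is at least as precise as either alternative.

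The Aim 1 power statement is under-reported, not shown to be in error. Its SD, correlation, ICC range, alpha, number of service areas and detectable difference are missing. This point is an available improvement to the analysis and does not show that the design fails.

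**What to change.** 1. In the Intent to Treat Analysis section, make follow-up reversible risk the outcome and add index reversible risk as a covariate. Alternatively, keep index and follow-up values as repeated outcomes with the arms constrained equal at index. State which is used, and on what scale index risk enters the count model.
2. Do the same for the other outcomes, each with its own index value.
3. In Statistical Power, report for Aim 1 the SD, correlation, ICC range, alpha, number of service areas and patients, and the resulting difference detectable with 80% power under the model to be fitted.

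The cost is one covariate per model and a few sentences. No extra clinics, patients or data collection are needed.

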#### **Qualitative Data**

Using a realist approach our process evaluation will explore "what works, for whom and in what circumstances" related to uptake/impact of the CDS system. It will be guided by our logic model and the TAM's conceptualization of the relationship between user perception and CDS acceptance/use. We will identify mechanisms of change (barriers/facilitators; impact of implementation strategy) at the clinician and health care system levels and assess how contextual factors impact outcomes. **Supplement Addendum**: The parent study involves assessing how CV Wizard is used at in-person

visits. We will account for the shift to VC by adding qualitative data on its use in VC. As in the parent study, process evaluation will be informed by the Technology Acceptance Model to understand (1) how CVD care takes place in VC and (2) the role of CDS in VC.

We will triangulate process data from all sources for a deep understanding of CV Wizard's acceptance/use in the CHCs. We will look at areas of consistency/inconsistency in these data (where different data sources show the same thing, or do not). A grounded theory approach coupled with an immersion-crystallization process will be used to identify themes and patterns in the qualitative data. We will emphasize factors influencing use of CV Wizard and its impact on care decisions. Data collection and analyses will be parallel and iterative, letting us identify salient constructs and knowledge gaps while implementation is ongoing. The study team will meet regularly to discuss and integrate qualitative and quantitative process evaluation and outcome data to help identify factors that affect success. The integration of mixed methods data will provide a more complete, nuanced understanding of the impact and use of the CV Wizard system than either method alone, and permit examination of the reliability and validity of the data sources. Supplement Addendum: Supplement data will be added to an existing NVIVO database to allow integration of findings. It will also be flagged to facilitate sub-analyses specific to this supplement's goals. To incorporate data from this study while allowing new themes to be considered, we will use an immersioncrystallization process which entails multiple iterations of data immersion, reflection, and code development and application, to identify new data themes or patterns related to the use of CV Wizard, and its impact on CVD risk management, in the VC context.

## b. Sharing of Results with Subjects

If the CV Wizard decision support tool is used during a patient encounter, the provider has the option to print the provider-facing report. If the provider wishes to discuss the results with the patient, he/she may print the patient-facing report and give a copy to the patient or post to clinic's patient portal (if available). To ensure patient confidentiality (i.e., the correct patient receives the printout), the patient's name is printed on the top of the report.

### c. Data and Specimen Banking

Not applicable.

### 8. Privacy, Confidentiality, and Data Security

## Quantitative Data Management, Sharing and Protection

OCHIN uses safeguards similar to those used at CHR to ensure confidentiality when handling data. All patient-related study data will be de-identified and unique patient identification codes will be used, and all data sources will be linked through a secure relational database at OCHIN. Data sent to CV Wizard, and then returned to OCHIN for analysis, will be de-identified and protected as described in the Security Measures section below. Only aggregate data will be shared with CHR through a secure data transfer web site, as necessary. The CV Wizard CDS system is a web service that uses input EHR data to identify eligible patients, compute CV risks, prioritize CV risk reduction, and provide treatment recommendations based on a complex set of evidence-based algorithms. A web-

based display of the results is then provided to the primary care providers.

### Qualitative Data Management, Sharing and Protection

Qualitative data will be securely stored at both CHR and OCHIN. All data work will be done on password-protected workstations, in a secure environment (HIPAA-compliant). At CHR, only study team members have access to the saved data. At OCHIN, access to study data is limited to the research department.

Data will be catalogued within 1 week of collection and will be entered in QSR NVivo. Data sharing agreements/protections will be set as necessary, and electronic data transfers will use a secure website or encrypted email. Hard copies of fieldnotes will be stored in a locked office at KPCHR that only research staff can access.

Audio recordings of staff/patient interviews will be stored on a secure file server that is accessible via password protected computers. Audio recordings will be transcribed by a KP/CHR-approved vendor. Audio files and transcripts will be transferred between CHR and the transcriptionist using a secure file transfer website. All audio files will be destroyed at the end of the study.

When research staff travel to/from the case study site clinics, they will follow the CHR procedure for physically moving data. The data being transferred may include encrypted audio recordings and notebooks containing fieldnotes (e.g., observation date/time, provider/staff name, patient encounter activity, etc.). Because clinic visits may take place at various locations and times throughout the day, there may be some instances (e.g., early morning or late afternoon/evening) that necessitate study staff transporting study materials to their home. In these cases, staff will:

- (1) Place all data in a secured pouch with the appropriate labeling outlined in the CHR procedure for physically moving data.
- (2) Transport data in the trunk of their vehicle and commute directly home.
- (3) Bring the data into their home and place in a secure location.
- (4) Transport data directly to KPNW facility.

## Storage of Recruitment Data

As outlined in Section 5.e (Case Study & Supplement Site Recruitment), we may identify patients for qualitative interviews using a BPA alert in the EHR (where providers flag patients), by pulling data on smartphrase use in the after-visit summary (AVS) that indicates CV Wizard was used during an encounter, or other indicators of tool use (e.g., CVW output was viewed or printed). In these cases, patient data will need to be accessed and stored for recruitment and tracking purposes. We will store the following data in OCHIN's instance of REDCap: patient name, encounter date, referring provider, clinic name, mailing address, phone number, email address, call attempts, interview completion, gift card distribution, and notes entered by the study team related to recruitment efforts (e.g., outreach type, date of outreach, etc.). OCHIN and KP CHR staff will have access to participant data in REDCap to make initial contact with participants. KP CHR staff participating in data collection will be given access to only the minimum necessary information. Access will be controlled in the Data Viewing Rights section of RedCap. This data will not be transferred or stored in any other location outside of REDCap.

#### Additional Information about Sensitive Data

We plan to pull data related to mental health diagnoses (depression, anxiety, and severe mental illness) to determine whether it explains variance in CV Wizard tool use. This data will be pulled

from the EHR (i.e., this information will *not* be collected directly from patients that are participating in the qualitative interviews). We will follow the same safeguards for this sensitive data as we do for all data collected in this study (see sections on data management, sharing, and protection; confidentiality; and security). This data will be collected (as applicable) for all clinics participating in the study. Given that individual patients are not enrolled for this aim of the study, there is no consent form or PRA to which this information should be added. NOTE: Each OCHIN member clinic has business use agreements with OCHIN to handle and manage PHI from their clinical data, and each CHC agrees that their electronic health record data may be used in research as part of their membership agreement.

### **Confidentiality Measures**

All CHR investigators and project staff, all HealthPartners data managers, and all OCHIN staff who work on research projects and handle human subjects data/have human subjects contact, sign confidentiality pledges and receive IRB and HIPAA training/certification.

### **Security Measures**

Multiple measures are in place to ensure the security of PHI. Data transfer to and from the EHR (at OCHIN), the web service (at Health Partners), and the web display (accessed at OCHIN member CHCs) uses a Simple Object Access Protocol (SOAP) with Secure Sockets Layer (SSL) encryption over a Hypertext Transfer Protocol Secure (HTTPS) computer network. There is a double firewall in the Web service so that once the data flow through the initial Web service firewall, the data cross another firewall into a new secure pathway that once again employs SOAP, SSL, and HTTPS to process the data and provide recommendations. This includes sending the data through a batch server for more efficient processing, but all within the double-firewall Web service. Limited clinical data for all adults are initially extracted from the EHR to determine CDS eligibility.

We estimate that 15-25% of study clinic patients may meet the eligibility criteria at which point more clinical information is extracted and full processing through the CV Wizard clinical algorithms occurs and is displayed back to the providers. If/when the CV Wizard tool is used, to ensure patient confidentiality, the name of the patient is printed on the CDS sheet given to the patient and their care provider at the clinic visit. This is needed to avoid mixing up printed pages and giving protected health information (PHI) to the wrong patient. It is also desirable to have each patient's name on this sheet of paper to assure the patient that the information on the paper is related to their own health state and not someone else's. The technical aspects of this system are also relevant; the printout is controlled from the CDS Web site, so the Web site must have the patient's name and other PHI.

With the analytic databases, measures will be taken to protect PCPs and patients from the risk of breach of confidentiality: A unique study ID code unrelated to the EHR record number or other study subject-specific information will be assigned to each patient and provider study subject and used to link data from various sources needed for analysis. A crosswalk table linking this code number to a provider PCP or patient name or medical record number will be destroyed within 12 months of completion of the linked databases needed for study analyses. To minimize the risk that a PCP will act wrongly on the basis of information provided through CDS developed for this study, communication to providers will have a written explanation that the CDS is a suggestion, not a mandate, and that the action should only be taken if judged to be clinically appropriate by the treating provider on the basis of the patient's current clinical status and preferences.

